8.5 Supplementary analysis under the treatment policy estimand

The co-primary endpoints will be evaluated under the treatment policy estimand during DB period. The treatment policy estimand includes data collected after discontinuation of study treatment regardless of rescue by surgery or SCS use for CRSwNP. Because these data will be analysed by ANCOVA for repeated measures which implicitly accounts for missing data under the MAR assumption, no imputation will be conducted for the missing data. The treatment policy estimand evaluates the treatment effect at the planned endpoint of the study, regardless of the treatments that patients actually received.

The analysis will be conducted using ANCOVA for repeated measures with treatment arm, baseline scores (baseline total NPS for NPS model and baseline NBS for NBS model), visit, region, CCI and treatment×visit as covariates. The variance-covariance matrix will assume to be unstructured. If the procedure does not converge, then the Toeplitz, first-order autoregressive, and compound symmetric structure of variance-covariance matrices will be tried in that order. The estimate of the treatment effect will be based on a contrast from the repeated measures ANCOVA model.

It is noted that if the primary analysis is statistically significant, it is not necessarily expected that all sensitivity and supplementary analyses will also give statistically significant results. If the results of the sensitivity/supplementary analyses provide reasonably similar estimates of

the treatment effect to the primary analysis, this will be interpreted as providing assurance that neither the lost information nor the mechanisms which cause the data to be missing have an important effect on primary analysis conclusions. Based on these outputs and the drug's mechanism of action, the plausibility of the assumptions that are made about missing data in the different analyses will be considered and described in the clinical study report.

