The primary database lock will occur after all randomised patients have been followed up for the 56-week DB treatment period. The study will remain blinded until the primary database lock. The final database lock will occur after the last patient completes the OLE. The primary analysis of efficacy endpoints will include all data captured during the double-blind-treatment period (intention-to-treat approach).

The primary analysis will compare the effect of benralizumab versus placebo on the change from baseline in total NPS at Week 56 (V11) and the change from baseline in bi-weekly mean NBS at Week 56 using a hybrid method of the worst-possible/worst-observation carried forward and multiple imputation, followed by an analysis of covariance (ANCOVA) with treatment arm, baseline scores of corresponding endpoint, region, and baseline CCI status CCI as covariates. Analyses for key secondary endpoints (i.e. change from baseline in DSS, LMS, and SNOT-22 at week 56) will be analysed using ANCOVA in a similar manner to co-primary endpoints.

A hierarchical fixed-sequence testing strategy will be used to control the overall type I error rate at the 0.05 level to account for multiplicity in testing for the co-primary endpoints and the 3 key secondary endpoints in the primary population.

[figure not shown]
Approximately 250 patients will be randomised to benralizumab or placebo in a 1:1 ratio. Assuming a population standard deviation of 2 in total NPS and 1 in NBS, this sample size will provide at least 80% power to detect a true mean (population) treatment difference of 0.85 units in total NPS and a difference of 0.4 in NBS with a two-sided 0.05 alpha level.

All safety parameters will be analysed descriptively. Data collected from the OLE will be analysed descriptively.

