7.1.1. Procedures for discontinuation of study treatment

At any time, patients are free to discontinue IP without prejudice to further treatment. A patient that decides to discontinue IP should always be asked about the reason(s) and the presence of any AEs.

All patients who prematurely discontinue IP during DB period should return to the study site and complete the procedures described for premature IPD visit within 8 weeks after the last dose of IP. At that visit, although no longer on IP, patients should be encouraged to remain in the study to complete all subsequent study visits, procedures, and assessments. Data collection should continue according to the study protocol. Note that in this case, the IPD visit replaces the nearest regular visit while the following visits continues until V11 week 56.

If the patient does not agree to complete all subsequent visits and procedures, the patient should be encouraged to stay in the study, keep the ePRO device, and continue selected visits until Week 56.

If the patient does not agree to continue in-person study visits, telephone visits should be performed to ensure the collection of endpoints and safety information. Patients will be encouraged to keep the ePRO device and do assessments, participate in the telephone visits, and return the ePRO device at the end of the DB period (Week 56). If a patient is not willing

to complete ePRO procedures, device should be returned at the IPD visit and the telephone follow-up visit should be continued. A patient that agrees to a modified follow-up visit is not considered to have withdrawn consent or to have withdrawn from the study. The decision on the selected follow-up option needs to be documented in the patients' medical records.

If a patient is not willing to participate further in the study after the IPD visit, the ePRO will be returned at the IPD visit. No further follow up visit is required after the IPD visit.

If patient decides to discontinue IP during OLE, he/she needs to complete the IPD visit at 8 weeks after the last dose of IP, and no further follow-up visit is required.

The reason for premature discontinuation of IP should be recorded in the eCRF.

See the SoA for data to be collected at the time of treatment discontinuation and follow-up and for any further evaluations that need to be completed.

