9.2. Sample size determination

The primary analysis will compare the effect of benralizumab vs placebo on the change from baseline in total NPS at Week 56 and on the change from baseline in bi-weekly mean NBS at Week 56 using a hybrid method of the worst-possible/worst-observation carried forward and multiple imputation, followed by an analysis of covariance with treatment arm, baseline scores of corresponding endpoint, region, and baseline CCI status (CCI) as covariates.

Approximately 250 patients will be randomised into SC benralizumab 30 mg or placebo in a 1:1 ratio.

The sample size was estimated based on a two-sided t-test at a significance level of 0.05. Assuming a population standard deviation of 2 in total NPS and 1 in NBS, this sample size will provide an overall 80% power to detect a true mean (population) treatment difference of 0.85 units in total NPS and a difference of 0.4 in NBS with a two-sided 0.05 alpha level.

Based on the assumptions above, the minimum observed mean difference that would be statistically significant at the 0.05 level is – 0.50 in total NPS and – 0.25 in NBS.

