1.4 Number of patients

The primary analysis will compare the effect of benralizumab vs placebo on the change from baseline in total NPS at Week 56 and on the change from baseline in bi-weekly mean NBS at Week 56 using a hybrid of worst-possible/worst-observation carried forward and multiple imputation (MI), followed by an analysis of covariance (ANCOVA) with treatment arm,

baseline scores of the corresponding endpoint, region, CCI [REDACTED] as covariates (See Section 4.2.5.1 for details).

Approximately 250 patients will be randomised into SC benralizumab 30 mg or placebo in a 1:1 ratio.

The sample size was estimated based on a 2-sided t-test at a significance level of 0.05. Assuming the population standard deviation (SD) of change from baseline is 2 for total NPS and 1 for NBS, this sample size will provide an overall 80% power to detect a true mean (population) treatment difference of 0.85 units in total NPS and a difference of 0.4 in NBS with a two-sided 0.05 alpha level.

Based on the assumptions above, the minimum observed mean difference of the changes from baseline between benralizumab and placebo that would be statistically significant at the 0.05 level is -0.50 in total NPS and -0.25 in NBS.

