- (b) Dropout Reason-based Multiple Imputation (DRMI): Assumes that the trajectory for patients in the benralizumab arm who dropped out for a treatment related reason and/or severe non-compliance of protocol is similar to that of patients in the placebo arm, whereas the remaining patients who has dropped out are imputed assuming MAR.

A summary of reasons for patients withdrawing from the benralizumab treatment arm and the corresponding treatment arm used to calculate the imputation under MAR, and DRMI are given in Table 12 .

Table 12 Parameters for calculating the imputation under MAR, and DRMI

Reason for withdrawal	MAR	DRMI
Adverse Event	Benralizumab	Placebo
Development of study-specific discontinuation criteria*	Benralizumab	Placebo
Death	Benralizumab	Placebo
Severe non-compliance to protocol	Benralizumab	Placebo
Eligibility criteria not fulfilled	Benralizumab	Benralizumab
Patient lost to follow up	Benralizumab	Benralizumab
Patient decision	Benralizumab	Based on review prior to study unblinding
COVID-19	Benralizumab	Benralizumab
Other	Benralizumab	Based on review prior to study unblinding

Note: Patients in the placebo arm are imputed using non-missing values in placebo arm.

*Development of study-specific criteria for discontinuation are based on the following: Anaphylactic reaction to the investigational product requiring administration of epinephrine; Development of helminth parasitic infestations requiring hospitalisation; A respiratory-related event requiring mechanical ventilation.

Some reasons for withdrawal are clearer to determine as treatment related (AEs, death, development of study-specific discontinuation criteria) or non-treatment related (patients lost

to follow up, eligibility criteria not fulfilled). Other reasons are less clear such as patient decision and 'Other'; a review of each patient who withdraws from the study will therefore be carried out prior to unblinding the study. Based on this review the default assumptions for DRMI as described in b), and Table 12 may be changed. A list of these patients and the assumptions made under DRMI will be documented prior to unblinding of the study.

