8.4 Supplementary analysis under the effectiveness estimand

A supplementary analysis will be evaluated under the effectiveness estimand. This analysis includes data collected up until the time of discontinuation from study treatment and excludes data if a patient has a surgery and/or SCS use for CRSwNP. Because these data will be analysed by ANCOVA for repeated measures which implicitly accounts for missing data under the MAR assumption, no imputation will be done after discontinuation from treatment or after rescue by surgery and/or SCS use for CRSwNP. This analysis evaluates the effect of initially assigned randomised treatment as long as the patient remains on treatment without being rescued by a significant alternate course of therapy such as surgery or SCS for CRSwNP.

The analysis will be conducted using ANCOVA for repeated measures with treatment arm, baseline scores (baseline total NPS for NPS model and baseline NBS for NBS model), visit, region, CCI and treatment×visit as covariates. The variance-covariance matrix will assume to be unstructured. If the procedure does not converge, then the Toeplitz, first-order autoregressive, and compound symmetric structure of variance-covariance matrices will be tried in that order. The estimate of the treatment effect will be based on a contrast from the repeated measures ANCOVA model.

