8.10 Efficacy estimands

Statistical Category	Estimand ¹			SAP Section
	Endpoint (Population)	Intercurrent Event Strategy ¹	Population Level Summary ¹ (Analysis)	
Primary objective: To evaluate the effect of benralizumab on nasal polyp burden and patient-reported nasal blockage				
Co-Primary/MCP	
 CFB in endoscopic total NPS (severe CRSwNP patients with asthma) CFB in bi-weekly mean NBS (severe CRSwNP patients with asthma) 	Included in analysis regardless of treatment discontinuation; WP after surgery for CRSwNP, WOCF after SCS use for CRSwNP ³ (primary estimand)	Mean difference between interventions at Week 56 ² (LSMD from CFB ANCOVA following hybrid WP/WOCF and MI)	Section 4.2.5.1
Supplementary and Sensitivity	
 CFB in endoscopic total NPS (severe CRSwNP patients with asthma) CFB in bi-weekly mean NBS (severe CRSwNP patients with asthma) 	
 Included in analysis regardless of treatment discontinuation or SCS use for CRSwNP; WP after surgery for CRSwNP⁴ Disc of treatment assumed based on DRMI³ Remained adherent to treatment without surgery or SCS use for CRSwNP⁵ (effectiveness) Included in analysis regardless of treatment discontinuation; surgery or SCS use for CRSwNP⁶, (treatment policy) 	
 Mean difference between interventions at Week 56² (LSMD from CFB ANCOVA following hybrid WP and MI) Mean difference between interventions at Week 56² (LSMD from CFB ANCOVA following hybrid WP/WOCF and DRMI) Mean difference between interventions at Week 56² (LSMD from CFB repeated measures ANCOVA) Mean difference between interventions at Week 56² (LSMD from CFB repeated measures ANCOVA) 	Appendix 8.2 Appendix 8.3 Appendix 8.4 Appendix 8.5
Key Secondary Objective: To evaluate the effect of benralizumab on sense of smell				
Secondary/MCP	CFB in bi-weekly mean DSS (severe CRSwNP patients with asthma)	Included in analysis regardless of treatment discontinuation; WP after surgery for CRSwNP, WOCF after SCS use for CRSwNP ³ (primary estimand)	Mean difference between interventions at Week 56 ² (LSMD from CFB ANCOVA following hybrid WP/WOCF and MI)	Section 4.2.6.1

Statistical Category	Estimand ¹			SAP Section
	Endpoint (Population)	Intercurrent Event Strategy ¹	Population Level Summary ¹ (Analysis)	

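### SAP 8.5 draws assurance about the missing-data mechanism from analyses that, apart from the partial DRMI analysis, assume missing at random

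*SAP*

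**What the plan says.** The primary analysis (SAP 4.2.5.1) uses multiple imputation under MAR for non-rescued patients with missing data. SAP 4.2.5.2 adds one sensitivity analysis, DRMI (8.3), and three supplementary analyses (8.2, 8.4, 8.5).

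Under DRMI, Table 12 imputes from the placebo arm for benralizumab patients who left the study because of an adverse event, study-specific discontinuation criteria, death or severe non-compliance. For the others, the text of 8.3 says "whereas the remaining patients who has dropped out are imputed assuming MAR". Table 12 keeps loss to follow-up, ineligibility and COVID-19 on the benralizumab arm. It sends patient decision and other reasons to a review before unblinding. That review may also change the table's defaults, and its assignments are to be documented before unblinding.

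The repeated-measures analyses in 8.4 and 8.5 are each described as a model that "implicitly accounts for missing data under the MAR assumption". Section 8.5 closes with the interpretation rule: similar estimates are to be "interpreted as providing assurance that neither the lost information nor the mechanisms which cause the data to be missing have an important effect" on the primary conclusions. SAP 8.10 labels the DRMI row "Disc of treatment assumed based on DRMI", whereas 8.3 works from withdrawal from the study.

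Protocol 7.1.1 separates the two events. A patient stops investigational product (IP), attends the IPD visit, and may then continue in full, continue with modified follow-up (including telephone only), or leave: "If a patient is not willing to participate further in the study after the IPD visit", no more visits are required. Modified follow-up does not count as withdrawal from the study.

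**The concern.** An analysis tests MAR only if it replaces MAR with something else while holding the estimand fixed. Three of the four analyses do neither. Agreement with them shows that the result is insensitive to how rescue or treatment discontinuation is handled, which is useful but is a different question.

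That leaves DRMI to carry the whole claim about the mechanism. Its force depends on how many benralizumab patients are switched to the placebo reference, and the plan does not fix that number. If few are switched, DRMI must land close to the primary estimate whatever the true mechanism is. The rule in 8.5 would still count that closeness as evidence of robustness. At stake is the robustness statement in the study report; the primary test itself is unaffected.

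**Working it through.** **1. The plan's own figures.** Inputs: "The sample size was estimated based on a 2-sided t-test at a significance level of 0.05" (SAP 1.4); "Approximately 250 patients will be randomised to benralizumab or placebo in a 1:1 ratio" (Protocol 1.2), so 125 per arm; "overall 80% power to detect a true mean (population) treatment difference of 0.85 units in total NPS and a difference of 0.4 in NBS" (Protocol 9.2); SD 2 for NPS and 1 for the nasal blockage score (NBS).

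- Minimum significant difference = 1.96 × SD × √(2/125): NPS 0.496, NBS 0.248. These match the stated 0.50 and 0.25.
- Power: NPS 91.9%, NBS 88.5%. The product under independence is 81.4%, consistent with the stated 80%.

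**2. What each analysis can test.**

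| Analysis | Missing-data assumption | Intercurrent-event handling against the primary |
|---|---|---|
| 8.2 | MAR | Changed (systemic steroid rescue) |
| 8.3 DRMI | Part placebo reference, part MAR | Same |
| 8.4 | MAR | Changed (discontinuation, rescue) |
| 8.5 | MAR | Changed (rescue) |

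**3. What DRMI covers in the benralizumab arm.**

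- Placebo reference: four withdrawal reasons.
- MAR: three reasons.
- Undecided until the review: two reasons, with no criterion written down.
- No Table 12 reason: patients off IP on modified follow-up who miss Week 56. This bears mainly on NPS, which needs an endoscopy; NBS may still be collected if the patient keeps the ePRO device.

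**4. How far DRMI can move the estimate.** Movement = share of the arm switched × average shift per switched patient. The documents give no dropout rate, so the shares and shifts are assumptions.

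- 10% missing, 2% switched, shift 0.7 NPS points: 0.02 × 0.7 = 0.014. All switched: 0.10 × 0.7 = 0.07.
- Full loss of the design effect (0.85), a quarter of the missing switched against all of them:

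| Missing | Quarter switched | All switched |
|---|---|---|
| 5% | 0.05 × 0.25 × 0.85 = 0.011 | 0.05 × 0.85 = 0.043 |
| 10% | 0.021 | 0.085 |
| 20% | 0.043 | 0.170 |

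**5. How large a departure would matter.** Tipping delta = (difference − minimum significant difference) / missing share, with the standard error held at its full-data value. Starting from the design differences (NPS 0.85, NBS 0.40):

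| Missing | NPS delta | NBS delta |
|---|---|---|
| 5% | 7.1 | 3.0 |
| 10% | 3.5 | 1.5 |
| 15% | 2.4 | 1.0 |
| 20% | 1.8 | 0.8 |

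NPS runs to 8 and NBS to 3, so the 5% row is practically out of reach. Nearer the threshold it is different. From an observed NPS difference of −0.60, the delta is (0.60 − 0.50)/0.10 = 1.0 point at 10% missing and (0.60 − 0.50)/0.20 = 0.5 at 20%. From an observed NBS difference of −0.325, it is (0.325 − 0.248)/0.10 = 0.77 at 10% missing.

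**The case against.** The plan has a fair defence. Protocol 9.4.1.2 promises sensitivity analyses that include missing-not-at-random assumptions using multiple imputation, and DRMI is one. No document promises a tipping point. SAP 8.3 gives a reason for keeping loss to follow-up and ineligibility at MAR: they are taken as unrelated to treatment. SAP 8.1 plans summaries of discontinuation and withdrawal reasons and a Kaplan-Meier plot of time to discontinuation. Straight after the assurance rule, 8.5 says that the report will discuss how plausible the assumptions are. The responder analyses in 4.2.5.4 count missing as non-response, which is not MAR. The assurance sentence also covers lost information, on which 8.2, 8.4 and 8.5 bear in part.

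Most of this stands, but it does not turn a MAR analysis into a test of MAR. The responder analyses are supportive, use a dichotomised outcome and are not among the analyses in 4.2.5.2. The planned discussion of plausibility softens the rule without replacing it.

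Three stronger readings are tempting, and the documents do not support them.

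- A reader might infer that every withdrawal outside the four placebo-referenced reasons stays at MAR. Patient decision and other reasons go to a documented review, which can assign them to placebo. The gap is that the review has no stated rule.
- A reader might infer that off-drug benralizumab patients are imputed as if still treated. The imputation in 4.2.5.1 works by randomised arm, includes data collected after IP discontinuation, and conditions on the patient's own earlier values. IP status is not a stated covariate, but the model is not restricted to on-drug data.
- A reader might infer that a placebo reference for all withdrawals would overturn the result. With 10% missing and a 0.7-point shift, −0.60 becomes −0.53, still beyond −0.50.

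**Conclusion.** The point holds in this limited form: the assurance rule in 8.5 claims more about the missing-data mechanism than the listed analyses can show. One of the four departs from MAR, and the share of missing data it covers is not fixed in advance. In the illustration, DRMI moves NPS by 0.014 to about 0.02 at 10% missing, against 0.07 to 0.085 if every missing patient is switched, so close agreement may carry little information.

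The practical weight depends on the result. At the design difference and 10% missing, it would take about 3.5 NPS points or 1.5 NBS points per missing benralizumab patient to lose significance, and few would doubt the finding. Near −0.60 on NPS, 0.5 to 1.0 point would do at 20% to 10% missing. The missing shares, switched shares, shifts and observed results are assumptions; only the design differences and thresholds come from the documents. The wording difference between 8.3 and 8.10 is clerical by itself.

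**What to change.** 1. In SAP 8.3, prespecify a delta-adjusted tipping-point analysis for both co-primary endpoints. Apply it to all non-rescued benralizumab patients with missing Week 56 data, whatever the withdrawal reason and including those with none. Add a worsening delta to their imputed Week 56 values in the 100 saved datasets, refit the ANCOVA, combine by Rubin's rules, and report the delta at which each p-value reaches 0.05. State the grid in advance and whether shifted values are capped at 8 and 3.
2. Have the blinded review of patient decision and other reasons use the recorded reason for IP discontinuation, and write that rule into 8.3.
3. In 8.5, limit the assurance about the missing-data mechanism to DRMI and the tipping point. Describe 8.2, 8.4 and 8.5 as showing sensitivity to the handling of intercurrent events.
4. Align the DRMI wording in 8.10 with 8.3.

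Placebo-based imputation for every off-IP withdrawal is a possible addition but more debatable, and it is not needed if the tipping point is in place.

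Cost: SAP wording and re-use of the existing imputation code, with a little more analysis work and no new data. The stated robustness may turn out less favourable.

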8.6 Handling incomplete dates for adverse events and medications

8.6.1 Partial dates for adverse events and prior/concomitant medication

Dates missing the day, or both the day and month of the year will adhere to the following conventions to classify AEs and to classify prior/concomitant medications.

